Analysis Plan

Study Title: Using Social Connectedness to Increase Physical Activity

Identifier: NCT04573972

Unique Protocol ID: STUDY2019_00000296

Date: October 22, 2021

Hypotheses

Hypotheses are pre-registered at ClinicalTrials.gov NCT04573972

<https://clinicaltrials.gov/ct2/show/NCT04573972>

We hypothesize that, compared to the regular incentive condition, participants in the social incentive condition will show a larger positive change in daily steps walked during the baseline period to daily steps walked in the post-intervention period.

Study Design

Participants volunteered for the study with a friend; thus randomization occurs at the level of the dyad, with half the dyads assigned to the regular incentive condition and half to the social incentive condition. During a 5-week protocol, participants complete a 1-week baseline period, a 2-week incentive period and a 2-week post-incentive period.

Communication with participants occurred using the Way to Health (W2H) platform. Participants downloaded the FitBit and Aware apps onto their IOS or Android smart phone to track steps walked and GPS location. They completed surveys on W2H at the beginning and end of the survey. W2H sent participants text messages each morning and evening. During the baseline period participants earned \$1 for each day they synced both apps. After the baseline period all participants were assigned a daily step goal that represented a 30% increase in daily steps walked. During the incentive and post-incentive periods, the evening text message included a link to a survey where participants could self-report walking with their partner. During both of these periods, participants earned \$1 per day for syncing the apps and an additional \$1 per day for completing the evening survey. During the incentive period only, they earn \$2 per day for meeting their step goal (regular incentive) or they earn \$1 per day for meeting their step goal and an additional \$1 per day for walking at least 1 mile with their partner. At the completion of the study, participants were mailed a ClinCard debit card loaded with their payment total.

Randomization

Simple randomization to condition was accomplished via the W2H platform at the completion of the baseline period. Because W2H does not have the capacity to randomize at the level of the dyad, the research team manually adjusted conditions such that both members of a dyad were in the same study condition.

Explanation of existing data

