2. The mean daily followup period step count (averaged across all of a participant's included followup period days) minus the mean daily baseline period step count (averaged across all of a participant's included baseline period days).
3. Number of days during treatment period when participant reached goal. Converted to a fraction by dividing by the number of included treatment period days.
4. Number of days during followup period when participant reached goal. Converted to a fraction by dividing by the number of included followup period days.
5. Change in score on UCLA Loneliness Scale. Score on post-test (range 0 to 60) minus score on pretest.

Secondary dependent variables (as pre-registered on Clinical Trials)

6. Number of days participant walked together with partner during treatment period, as assessed via self-report on daily survey

7. Number of days participant walked together with partner during followup period, as assessed via self-report on daily survey
8. Number of days participant walked together with partner during treatment period, as assessed via Aware data
9. Number of days participant walked together with partner during followup period, as assessed via Aware data

Indices

The UCLA Loneliness Scale is measured on both the intake and exit surveys. It consists of 20 items, each scored as 0, 1, 2, or 3. The scores from all 20 items are added to form a total score ranging from 0 to 60.

Inclusion Criteria

In order to be included in the study, each participant must fulfill all of the following

- Consent
- Fully enroll, including authorizing FitBit app and installing Aware app
- Link to a friend who fully enrolls in the study before the registration deadline
- Participants who request to unenroll are excluded.
- Provide synced step data for at least one day of the 7-day baseline period
 - That is, there must be at least one baseline day with a non-zero step count
- Provide Aware data for at least one day of the 7-day baseline period

Exclusion of individual data points

- Days that a participant has a value of 0 for steps walked will be considered missing data (assume there was no sync for that day)
- For each participant, we will compute the mean and standard deviation of number of daily steps, computed over all days of the study with non-zero step counts. Days with a step count that are > 3 standard deviations away from the participant's own mean will be excluded from analyses (treated as missing data).

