- Average step count will then be computed for each phase, after treating these excluded data points as missing.

Data File Structure

- Note: remove the research team participants from the datafile.
- Daily file (35 rows per participant -- one row per day of the protocol)
 - Subject id
 - Dyad id (links together the two subject ids in a friend pair)

- Phase (baseline, incentive, followup)
- Day of protocol (1 - 35)
- Calendar date
- FitBit steps walked
- Met goal (yes or no; missing for baseline period)
- Synced FitBit data (yes or no)
- Synced Aware data (yes or no)
- Correct end-of-day survey sent (yes or no; missing for baseline period)
- Answered end-of-day survey (yes or no; missing for baseline period)
- Walked with partner (yes or no; missing if wrong survey sent or survey not answered)
- Walked at least 2,000 steps with partner (yes, no, or missing)
- Walked in-person or virtually with partner
- Study file (1 row per participant)
 - Subject id
 - Included in study (for ITT analysis)
 - Included in main analysis
 - Dyad id (links together the two subject ids in a friend pair)
 - Date started baseline period
 - Date started incentive period
 - Goal number of steps
 - Total amount earned during study
 - All responses from baseline survey
 - All responses from exit survey

ITT analysis

- Includes all Ss who meet the inclusion criteria, even if they have a lot of missing data.
- Similar to the main analysis described below, but it doesn't exclude Ss based on missing data.
- It does still exclude individual data points, same as in the Main Analysis

Main Analysis

In order to be included in the main analyses, each participant must also fulfill all of the following

- Provide synced step data for at least 2 days of the 7-day baseline period
- Provide synced step data for at least 4 days of the 14-day treatment period
- Provide synced step data for at least 4 days of the 14-day followup period
- Be paired with a partner who is also included in the main analyses

Secondary Analyses

- Secondary analyses will explore the relationships among change in UCLA Loneliness score (intake to exit survey), change in mean daily steps walked from baseline to post-incentive period, and percentage of days during post-incentive period when the dyad walked together. Specifically, we will test whether the effect of study condition on change in steps walked is mediated by change in loneliness score and percentage of days when the dyad walked together.

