- Two boot-strapped mediation analyses will be conducted, one for each putative mediator.

Primary dependent variables (as pre-registered on Clinical Trials)

1. The mean daily treatment period step count (averaged across all of a participant's included treatment period days) minus the mean daily baseline period step count (averaged across all of a participant's included baseline period days).
2. The mean daily followup period step count (averaged across all of a participant's included followup period days) minus the mean daily baseline period step count (averaged across all of a participant's included baseline period days).
3. Number of days during treatment period when participant reached goal. Converted to a fraction by dividing by the number of included treatment period days.
4. Number of days during followup period when participant reached goal. Converted to a fraction by dividing by the number of included followup period days.
5. Change in score on UCLA Loneliness Scale. Score on post-test (range 0 to 60) minus score on pretest.

Secondary dependent variables (as pre-registered on Clinical Trials)

6. Number of days participant walked together with partner during treatment period, as assessed via self-report on daily survey
7. Number of days participant walked together with partner during followup period, as assessed via self-report on daily survey
8. Number of days participant walked together with partner during treatment period, as assessed via Aware data
9. Number of days participant walked together with partner during followup period, as assessed via Aware data

Main Analysis

- DV = each of the primary dependent variables shown above
- IV = condition (regular vs. social incentive)
- Data structure: 1 rows of data per participant
- Errors clustered at the dyad level
- Covariates:
 - Partners in same or different time zone (dyad level)
 - Gender, age (individual level)
 - Date of first day of baseline (individual level)
 - Lag in number of days between enrollment of first partner and enrollment of second partner (dyad level)

Exploratory HLM Analysis

- DV = daily step count
- IV
 - Fixed effect of participant
 - Dummy variable for treatment period (relative to baseline period as reference)
 - Dummy variable for followup period (relative to baseline period as reference)
 - Interaction between each dummy & condition (regular vs. social incentive)
- Data structure: 35 rows of data per participant (one for each day)

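### Neither mediator is measured before the follow-up step outcome accrues, so the planned mediation test cannot show mechanism and, for joint walking, can readily report mediation that is not there

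*SAP*

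**What the plan says.** The SAP section Secondary Analyses sets the outcome of the mediation models as "change in mean daily steps walked from baseline to post-incentive period". It first describes the work as exploring relationships, then commits to a test: "we will test whether the effect of study condition on change in steps walked is mediated by change in loneliness score" and by joint walking.

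The joint-walking mediator is the "percentage of days during post-incentive period when the dyad walked together". For loneliness, the Indices section states that "The UCLA Loneliness Scale is measured on both the intake and exit surveys", and no other occasion is listed. Study Design says "They completed surveys on W2H at the beginning and end of the survey"; I read the last word as study, so the exit score comes after follow-up.

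On method the SAP adds only this: "Two boot-strapped mediation analyses will be conducted, one for each putative mediator". For these models it states no temporal ordering, adjustment set, resampling unit, reverse model or sensitivity analysis. Joint-walk days in the treatment period are collected (secondary variables 6 and 8) but are not used as a mediator.

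**The concern.** A mediation claim says that condition changed the mediator and that the mediator then changed the outcome. That needs the mediator to be settled before the outcome, and no common cause of the two left unadjusted. Here joint walking is counted on the same days as the outcome, and loneliness is scored after those days. An association between mediator and steps within arms could therefore arise in three ways: the mediator raised steps, steps raised the mediator, or a generally more active dyad has more of both. A bootstrap interval for the indirect effect describes sampling error and does not distinguish these.

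This is the plan's only test of mechanism. A significant result would naturally be read as evidence that walking together, or feeling less lonely, is what moved activity.

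**Working it through.** **Inputs from the documents.** Periods of 7 + 14 + 14 = 35 days, so follow-up is days 22 to 35. Enrolment cap 220 people, so at most 220 / 2 = 110 dyads. Half the dyads per arm; alpha 0.05. The plan gives no effect size, SD or power figure for these analyses, so there is nothing of its own to reproduce.

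**Assumptions.** The analysed number is not given, so 80 dyads was run as well as 110. The estimator is not named; I take the usual indirect effect a·b, where a is the effect of condition on the mediator and b the slope of the outcome on the mediator given condition.

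**Mediator as a pure consequence (loneliness).** Let c be condition, Y = τc + u and M = sY + e, with no path from M to Y.

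- a = sτ
- b = s·var(u) / [s²var(u) + var(e)]
- a·b/τ = s²var(u) / [s²var(u) + var(e)] = r², the squared within-arm correlation

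Thus r = 0.3 gives an apparent mediated share of 9% and r = 0.5 gives 25%, with true mediation zero. This is a share, not the chance of a significant test. If τ = 0, then a = 0 and the product vanishes.

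**Mediator sharing an activity level with the outcome (joint walking).** Let Y = u and M = αc + γu + e. Condition has no effect on steps, and joint walks only replace solo walks.

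- a = α
- b = γ·var(u) / [γ²var(u) + var(e)]
- a·b is non-zero whenever α and γ are, offset by a spurious direct effect of −a·b

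This route needs no condition effect on steps.

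**Simulation.** 600 trials per scenario, 400 bootstrap samples by dyad, 95% percentile interval for a·b. The mediator never affects steps. For loneliness, d is the condition effect on steps in SD and r the strength with which steps lower loneliness. For joint walking, the total effect on steps is zero, the log OR is the condition effect on joint-walk days, and the slope is log-odds per unit of dyad mean step change.

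| Scenario | 110 dyads | 80 dyads |
|---|---|---|
| Joint walking, follow-up; log OR 0.3, slope 0.3 | 22.5% | 13.2% |
| log OR 0.6, slope 0.3 | 48.2% | 34.7% |
| log OR 0.6, slope 0.5 | 84.0% | 65.8% |
| log OR 0.9, slope 0.5 | 91.5% | 80.5% |
| Loneliness; d 0.3, r 0.2 | 6.5% | 3.5% |
| d 0.3, r 0.3 | 10.2% | 9.5% |
| d 0.4, r 0.2 | 8.3% | 3.8% |
| d 0.4, r 0.3 | 14.3% | 14.5% |
| d 0.5, r 0.3 | 21.7% | 17.0% |
| Joint walking, treatment period, unadjusted; slope 0.3 | 36.8% | 27.2% |
| slope 0.5 | 71.7% | 62.0% |
| Same, adjusted for treatment-period step change; slope 0.3 | 7.7% | 7.0% |
| slope 0.5 | 4.3% | 6.3% |

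With a mediator unrelated to steps the rate was 0.2 to 6.3% (110 dyads) and 0 to 3.5% (80 dyads). The simulation error at a true 5% is √(0.05 × 0.95 / 600) = 0.9 points.

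The treatment-period rows use a log OR of 2 × 0.6 = 1.2, because the social arm is paid for joint walking then. In that model the two step changes correlate at 0.485 / √(0.65 × 0.61) = 0.77. With assumed correlations of 0.5 to 0.7 instead, moving the window alone gave 28 to 58% (80 dyads) and 36 to 81% (110 dyads); with the adjustment the rate was 2.5 to 7.5%.

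**Collinearity of the earlier mediator.** Suppose joint-walk rates of 20% against 61% or 80% in the treatment period, with a correlation between mediator and condition of about 0.76 or 0.89. The variance inflation 1/(1 − r²) is then about 2.4 or 4.8.

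**The case against.** The SAP introduces these analyses as exploring relationships and calls the mediators putative. That softens the claim, but the next sentence specifies a test of whether the effect is mediated, and the analyses are not placed under the separate Exploratory HLM heading.

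Joint walks may add steps rather than replace solo ones. This stands: the indirect path would then be real, though partly true by definition. The planned model cannot tell the two cases apart. For the same reason the overlap must not be overstated. A reader might multiply the 2,000-step field in the daily file by a 10-point arm difference in joint-walk days (0.10 × 2,000 = 200 steps per day) and call that artefact. If the walks add steps, that is a real indirect effect; if they replace solo walks, no steps are added. The SAP also does not say that the mediator uses that field.

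A reader might also infer that a positive result is to be expected for both mediators. The documents give no effect sizes to support that, and for loneliness the rate can stay near or below 5%.

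Finally, the hypothesis concerns post-intervention steps, so whether joint walking persists is a fair question. It is, and the post-incentive measure is worth reporting as a description.

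**Conclusion.** The point holds for both mediators as a defect of timing, and for joint walking also as a substantial risk of a false finding. Under the assumed effects, same-period joint walking gave significant mediation in 13 to 92% of trials although it had no effect on steps and the trial itself was null. The key assumptions are that condition raises joint walking in follow-up, which is plausible because the social arm was paid for it in the preceding period, and that more active dyads walk together more often. For loneliness the inflation is modest, and it requires both a condition effect on steps and an effect of steps on loneliness. The order cannot be recovered from two survey occasions.

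A reader might infer that an earlier mediator window is repair enough. It is not: 27 to 72% of trials still gave false mediation in the tabulated runs, because active dyads are active in both periods. Nor does the point reach the primary results; the randomised comparisons of condition do not depend on these models.

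**What to change.** Amend the Secondary Analyses section of the SAP as follows.

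1. Report the loneliness analysis and the post-incentive joint-walking analysis as associations, not mediation.
2. If a mediation test is kept, use the fraction of treatment-period days with a joint walk, derived from variables 6 and 8, as the mediator for follow-up step change. Adjust for treatment-period step change and resample whole dyads.
3. Add a reverse model and a sensitivity analysis for unmeasured confounding. In the simulation treatment-period step change captured all of the shared activity, which real data need not satisfy.

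The cost is SAP wording, on data already collected. Three downsides should be stated:

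- In the incentive period the social arm earns $1 per day for walking at least 1 mile with the partner, so this mediator partly measures uptake of the manipulation. It will be collinear with condition, which costs precision.
- It does not capture persistence of joint walking, so the post-incentive measure stays as description.
- The adjusted test does not count any effect of joint walking that runs through treatment-period steps.

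### The main model leaves out each participant's own baseline value (mean baseline steps, intake UCLA score), which may cost some precision, mainly for DVs 3–5

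*SAP*

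**What the plan says.** The second Main Analysis section of the SAP takes "DV = each of the primary dependent variables shown above", uses one row per participant and specifies "Errors clustered at the dyad level". Its covariates are whether partners share a time zone, gender, age, the calendar date on which baseline began, and the lag between the partners' enrolments. No baseline outcome value is listed.

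The five primary DVs use baseline in different ways:

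- **DVs 1 and 2** are a phase mean "minus the mean daily baseline period step count".
- **DVs 3 and 4** are goal-day proportions. DV 3 is "Converted to a fraction by dividing by the number of included treatment period days", and DV 4 is the follow-up equivalent. Under Study Design, the goal is a 30% rise in daily steps, assigned after baseline.
- **DV 5** is the post-test minus the pre-test UCLA score.

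The missing covariates are available. Under Data File Structure, the daily file holds "FitBit steps walked" for all 35 days, and the study file holds the baseline survey. Randomisation took place when baseline ended, and completing the intake survey was part of enrolling, so both values precede allocation.

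No other planned analysis adds the adjustment. The ITT analysis is "Similar to the main analysis described below". The Exploratory HLM Analysis uses a "Fixed effect of participant", which is again a within-person difference, and its DV is daily steps, so it does not cover DVs 3–5.

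**The concern.** The pre-treatment value of an outcome is often its best predictor, and here it costs nothing to use. A change score includes baseline but fixes its slope at 1. When the true slope of the later value on baseline differs from 1, noise from the baseline week stays in the outcome.

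The goal-day fractions subtract nothing. A participant with a chance-high baseline week receives a higher goal and reaches it less often, so baseline noise passes straight into DVs 3 and 4.

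Condition varies only between dyads. With 220 people fully enrolled there are at most 220/2 = 110 dyads, fewer after unlinked partners are removed, and no power calculation is given. Randomisation was simple and no stratification on baseline activity is described, so a chance imbalance in baseline steps would go uncorrected in DVs 3 and 4. Validity is not in question; the width of the intervals is.

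**Working it through.** The plan gives no power, effect size, SD, correlation or sync rate, so there is no figure of its own to reproduce. From the documents come 7 baseline days, 14 days in each later phase, a goal 30% above baseline, at most 110 dyads, and minimum baseline data of 2 days (main analysis) or 1 day (ITT). The rest is assumed.

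**DVs 1–2.** Let B be the baseline mean over m days and F the later mean over f days. Let sb be the between-person SD, sw the day-to-day SD, sc the SD of individual change, and g the average rise as a share of a person's own level.

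- Var(B) = sb² + sw²/m
- Var(F) = (1+g)²sb² + sc² + sw²/f
- Cov(B,F) = (1+g)sb², and slope β = Cov/Var(B)
- Share of variance saved by adjustment = (1−β)²Var(B) / Var(F−B)

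Assumed grid: sb 2000–3000, sw 3000–3500, sc 1000–2000 steps; central values 2500, 3250, 1500. With m = 7, f = 14, g = 0 and central values:

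- Var(B) = 6,250,000 + 10,562,500/7 = 7,758,929
- Var(F) = 6,250,000 + 2,250,000 + 10,562,500/14 = 9,254,464
- β = 6,250,000/7,758,929 = 0.806
- Var(F−B) = 9,254,464 + 7,758,929 − 12,500,000 = 4,513,393
- Saving = (0.1945)² × 7,758,929 / 4,513,393 = 6.5%, an SE about 3% narrower

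Condition is compared between dyads, so I repeated this for the variance of dyad means. Assumed partner correlations were 0.3 in level, 0.5 in change and 0 in day noise. The slope is still the individual-level one, so the dyad-level gain can fall below zero.

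| g | Individual: range (central) | Dyad mean: range (central) |
|---|---|---|
| 0 | 2.7 to 14.7% (6.5%) | 1.5 to 10.2% (3.9%) |
| 0.1 | 0.2 to 8.6% (2.2%) | −0.3 to 4.7% (0.6%) |
| 0.2 | 0.0 to 4.1% (0.2%) | −0.5 to 1.9% (−0.3%) |
| 0.3 | 0.0 to 5.2% (0.3%) | −0.6 to 8.2% (1.0%) |

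Fewer baseline days raise the gain. If 20% of participants have 2 days and the rest 7 (central values, no partner correlation), it is 11%, 6%, 2% and 0.3% at g = 0, 0.1, 0.2 and 0.3.

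**DVs 3–4.** These were simulated: goal = 1.3 × B, 7 baseline and 14 later days, daily steps floored at 0, mean 6000–9000 steps, same SD grid. The individual column is the squared correlation of B with the goal-day fraction. The dyad column is the reduction in dyad-mean variance with the same partner correlations.

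| g | Individual: range (central) | Dyad mean: range |
|---|---|---|
| 0 | 14–31% (19–23%) | 11–28% |
| 0.1 | 9–26% (13–18%) | 6–23% |
| 0.2 | 4–21% (8–12%) | 2–17% |
| 0.3 | 1–15% (4–7%) | 0–11% (central 2–4%) |

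If SDs instead scale with a person's activity level, the figures for g from 0 to 0.3 are 2–12% (individual) and 1–8% (dyad).

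**DV 5.** With equal intake and exit variances and correlation ρ, the change score has variance 2σ²(1−ρ) and the adjusted outcome σ²(1−ρ²). The ratio is (1+ρ)/2, so the saving is (1−ρ)/2: 25% at ρ = 0.5, 15% at 0.7, 5% at 0.9. A stable component p shared by partners multiplies this by (1−p); at p = 0.3 it is 17.5% at ρ = 0.5 and 3.5% at ρ = 0.9. Filling a share s of exit scores from intake, as the Missing data section provides, multiplies it by about (1−s); at s = 0.2 and p = 0 it is 20% and 4%.

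**Power.** Where the planned model has 80% power, variance savings of 5%, 10%, 15% and 25% give about 82%, 84%, 86% and 90%.

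**The case against.** The strongest reply is that nothing here is an error. Change scores with pre-listed covariates are a legitimate choice, and swapping one unbiased estimator for another is partly taste. The only stated hypothesis concerns change in steps from baseline to the post-intervention period, which is DV 2, where the gain is smallest. At the central values the dyad-level saving is at most 3.9%, an SE about 2% narrower, and at g = 0.2 adjustment is marginally worse. All of this stands. However, the SAP lists all five DVs as primary, and the case is stronger for the others.

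Three narrower points also have force:

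- DV 5 is a change score with the same algebra as DVs 1–2. It ranks with DVs 3–4 only because its variance is assumed stable while steps are allowed to grow in proportion. The ordering therefore depends on assumptions.
- The simulation sets the goal at exactly 1.3 times the analysed baseline mean. The analysed mean drops days by a 3-SD rule computed over the whole study, which could not have been applied when goals were assigned. The two means may differ, probably slightly.
- If outcomes have been seen, the practical result is one extra sensitivity table.

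These limit the size and the remedy. None supplies the missing adjustment or shows that adding it would do material harm.

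**Conclusion.** The concern holds. The main model omits two baseline values already in the data files, and neither the ITT analysis nor the HLM makes up for it. The cost is precision only. It is modest, and the documents cannot fix its size.

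For DVs 1–2 the loss may be nil: the 30% goal makes change proportional to baseline plausible, which brings the slope near 1. It grows if change is unrelated to level or if many participants have few baseline days. For DVs 3–4 it could be appreciable if activity rises little, and falls to a few percent if activity rises by about 30%. For DV 5 it depends on the intake–exit correlation, on similarity between partners and on how many exit scores are filled from intake. This is a worthwhile improvement, held with medium confidence, and not a flaw that invalidates the plan.

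**What to change.** Add mean daily baseline steps as a covariate for DVs 1–4 and the intake UCLA score for DV 5. Keep the DVs, the other covariates and the dyad-clustered errors. For DVs 1, 2 and 5 the condition coefficient then equals the ANCOVA estimate; for DVs 3–4 it is an ordinary baseline adjustment. Apply the same to the ITT analysis.

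If no outcome data have been seen, make this a documented amendment. If they have, keep the filed model as primary and report the adjusted model beside it as a labelled sensitivity analysis. Enrolment closed on Oct 11, 2020 and the documents are dated October 22, 2021, so the second route is probably the realistic one, although the SAP states that the plan was filed before any data were downloaded from the study platform.

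The cost is one degree of freedom per model, no new data, and a documented change to a filed plan or one additional table.

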The study protocol was pre-registered at ClinicalTrials.gov NCT04573972 <https://clinicaltrials.gov/ct2/show/NCT04573972> prior to any data collection. Clinical Trials pre-registrations do not include analysis plans. Consequently, this OSF pre-registration, including an analysis plan, was filed prior to downloading any data from W2H.

Participant flow diagram: ([name] or [name], please fill in numbers)

XXX people entered W2H portal	→ XX did not consent
↓ XX consented	→ XX did not fully enroll
↓ XX fully enrolled	→ XX not linked to a fully-enrolled partner
↓ XX has fully-enrolled partner	→ XX did not provide synced FitBit & Aware data for at least 1 out of 7 days of pre-intervention period or has partner who did not provide synced data for 1 out of 7 pre-intervention days
↓ XX provides baseline data	→ XX requested to be unenrolled prior to randomization
↓ XX included in study and randomized to condition (N= XX/2 pairs)	
↓ XX in the regular incentive condition & YY in the social incentive condition	

Data collection procedures

Study participants were recruited at Carnegie Mellon University through posting on the subject pool website and announcements to undergraduate classes. Potential participants had to sign up with a friend, with at least one member of the friend pair being a current CMU student. Participants had to own an IOS or Android smartphone and be willing to download the FITBit and Aware apps to track their activity and location for 5 weeks.

Stopping rule

Our stopping rule was to close enrollment once 220 people were fully enrolled or when Oct 15, 2020 occurs, whichever comes first. We opened enrollment on Oct 1, 2020 and closed it on Oct 11, 2020 because at that point 220 people had fully enrolled. Fully enrolling includes consenting, completing the intake survey, providing a code for a partner who was also enrolling, and downloading the FitBit and Aware apps. Some of the individuals who fully enrolled were not included in the study because their partner did not fully enroll.

Manipulated variables

There was one manipulated variable (treatment condition) with two levels: regular vs. social incentive.

Measured variables

Primary dependent variables (as pre-registered on Clinical Trials)

1. The mean daily treatment period step count (averaged across all of a participant's included treatment period days) minus the mean daily baseline period step count (averaged across all of a participant's included baseline period days).

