- Clustering: days nested within participant; participant nested within dyad

Transformations

None planned.

Inference criteria

Alpha is set at .05

Data exclusion

See analysis plan

Missing data

When a participant is missing step data for an individual day, the mean daily step count for the study phase will be computed using the days with non-missing data. If a participant is missing step data for all the days in a study phase, the mean daily step count for the baseline period will be substituted (leading to a change score of 0).

If a participant is missing data from the intake survey (e.g., gender, age, or UCLA loneliness score), the study-wide mean or mode will be substituted. If a participant is missing data from the exit survey (e.g, UCLA loneliness score), the corresponding value from the intake survey will be substituted.

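### Five equally ranked primary outcomes are each tested at .05 with no lead outcome, order or adjustment, though the one hypothesis written out concerns only follow-up steps

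*SAP*

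**What the plan says.** Under the heading that begins "Primary dependent variables (as pre-registered on Clinical Trials", the SAP lists five outcomes:

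- DV 1: mean daily steps, treatment period minus baseline
- DV 2: mean daily steps, follow-up minus baseline
- DV 3: fraction of treatment-period days at goal
- DV 4: fraction of follow-up days at goal
- DV 5: change in UCLA Loneliness score

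The protocol carries the same list. Nothing in it ranks one outcome above another.

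The SAP's second Main Analysis section, which gives the model, sets "DV = each of the primary dependent variables shown above" against a single two-level condition factor. That gives one test of condition per outcome and five in all. The Inference criteria section consists of one sentence: "Alpha is set at .05".

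The Hypotheses section, identical in both documents, states one expectation: that the social incentive arm "will show a larger positive change in daily steps walked during the baseline period to daily steps walked in the post-intervention period". That is DV 2. The section also refers to hypotheses registered elsewhere, so this description covers only what the two documents themselves contain.

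**The concern.** The plan has one written hypothesis, five primaries of equal standing, and no rule linking them. It does not say that one significant primary is enough for success, but nothing in it excludes that reading. Under that reading, .05 is the error rate of each test and not of the claim.

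A chance result on loneliness or on treatment-period goal days could be reported as a primary finding while the hypothesised outcome shows nothing. The design also makes different answers on different primaries plausible. It has "a 2-week incentive period and a 2-week post-incentive period", with the goal and partner-walking payments made only in the first of these, so treatment-period and follow-up outcomes may genuinely diverge. The reader then has no prespecified basis for deciding which one settles the question.

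**Working it through.** The plan gives no familywise error rate or power figure to reproduce.

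**Inputs.** Alpha is .05 (SAP, Inference criteria). There are five primary DVs with one test each (SAP, Main Analysis). Sidedness is not stated, so two-sided tests are assumed. The documents give no correlations between outcomes, so a range is shown.

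**Exact results when no outcome has a true effect**

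- At least one false positive among five independent tests: 1 − 0.95^5 = 1 − 0.7738 = 0.226.
- At least one false positive favouring the social arm, independent: 1 − 0.975^5 = 0.119, against 0.025 for a single test.
- At least one other primary significant while DV 2 is not, independent: 0.95 × (1 − 0.95^4) = 0.95 × 0.1855 = 0.176.
- Limit in which the four step outcomes act as one test, independent of loneliness: 1 − 0.95^2 = 0.0975. In the same limit, another primary is significant while DV 2 is not with probability 0.95 × 0.05 = 0.0475.

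**Allowing for correlation.** DVs 1 to 4 all come from the same daily step record, so positive correlation among them is expected. Test statistics were simulated as multivariate normal. The four step outcomes had equal correlation r, and each had correlation 0.05 with loneliness. Signs were aligned so that positive favours the social arm. Simulated figures are good to about 0.1 percentage point.

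| Assumption | Any false positive | Any favouring social arm | Another primary significant, DV 2 not |
|---|---|---|---|
| All five independent | 22.6% | 11.9% | 17.6% |
| r = 0.5 | 19.8% | 10.0% | 14.8% |
| r = 0.8 | 15.8% | 8.0% | 10.8% |
| r = 0.9 | 13.9% | 7.0% | 8.9% |
| Limit: four step DVs as one test | 9.75% | 1 − 0.975^2 = 4.9% | 4.75% |

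**Power under an adjustment.** A test with 80% power at two-sided .05 has a standardised effect of 1.960 + 0.842 = 2.802.

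- At .05/4 = .0125 the critical value is 2.498, and power is Φ(2.802 − 2.498) = 0.619.
- At .05/5 = .01 the critical value is 2.576, and power is Φ(2.802 − 2.576) = 0.589.

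**Not counted.** The ITT analysis repeats the tests on an overlapping set of participants. The four secondary DVs, the two mediation analyses and the exploratory HLM are also left out.

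**The case against.** The strongest reply is that the SAP makes no any-one-wins claim. If each DV is judged against its own null and all five are reported, each test has the error rate stated. Whether steps, goal attainment and loneliness need joint control is partly convention in a small behavioural trial. The written hypothesis already points to DV 2, and the mediation analyses use that same outcome. Selective reporting is limited because all five outcomes are listed in advance and the registration, "including an analysis plan, was filed prior to downloading any data from W2H", lets a reader apply a correction. Independence among four outcomes built from the same step counts is also unrealistic.

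Much of this is fair, and it limits the point. DV 2 taken alone is tested validly. The 22.6% is an upper figure for positively correlated outcomes, not an estimate, and no single value can be established without the correlations. Different assumptions, with correlations of 0.7 to 0.85 within a period and 0.4 to 0.55 across periods, give 17% to 19%.

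The gap remains. The SAP never says that DV 2 leads; it is listed second among equals. Hypotheses registered elsewhere may be more numerous, but the documents take no multiplicity rule from them. Listing outcomes in advance shows how many tests there were without saying which one decides. Loneliness is a survey scale and not derived from steps, so even in the limit there are two separate chances of a false positive.

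**Conclusion.** The concern holds. The error rate of a primary claim is undefined, and if any significant primary can support one, it is well above .05. With no true effects and two-sided tests it is at most 22.6% for non-negatively related outcomes, about 14% to 20% over the assumed correlations of 0.5 to 0.9, and still 9.75% in the most favourable case considered. The chance that another primary is falsely significant while DV 2 is not runs from 17.6% down to 4.75%. These figures rest on assumed correlations and on normally distributed test statistics. The missing rule itself can be read directly from the text. This should be fixed, but it does not invalidate the test of the stated hypothesis.

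**What to change.** Add one paragraph to the SAP's Inference criteria:

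- DV 2 (follow-up minus baseline mean daily steps) is the single lead primary outcome, tested at two-sided .05, and it carries the trial's conclusion.
- DVs 1, 3, 4 and 5 are tested by Holm's procedure at a familywise .05 only if DV 2 is significant. Otherwise they are reported as supportive.

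DV 2 loses no power. The smallest p-value among the other four must be below .0125, where a test with 80% power at .05 has about 62%. The gate also largely rules out a confirmatory claim for a treatment-period effect that fades by follow-up: if DV 2 is truly null, such a claim is possible in at most 5% of trials.

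If the sponsor wants to be able to make that claim, Holm should be applied across all five instead. The smallest p-value must then be below .01, where 80% power falls to about 59% at the strictest step, and DV 2 shares that cost. The choice belongs to the sponsor, but one of the two should be written down.

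If results have already been seen when the paragraph is added, the change should be dated and disclosed as not prespecified.
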